## Statistical Analysis

Categorical variables will be summarized by number and percent. Continuous variables will be summarized by total number (N), mean, standard deviation (SD), median, minimum and maximum. Ninety-five percent, 2-sided confidence intervals on estimated means and differences in means between treatment and control groups will be calculated (corrected for multiplicity where needed). Confidence intervals will be similarly computed for proportions and differences between proportions. In addition, propensity score and sensitivity analyses will be utilized to compare adverse events and adverse device effects incidence versus historical control. Wilcoxon signed rank tests, Fisher exact tests, and Pearson Correlations will be utilized to compare changes in baseline variables between varying time points of the study (e.g. Baseline versus Therapy) and to correlate stimulation parameters with endpoint values.

Markov-chain Monte Carlo Analyses will be utilized to conduct Bayesian posterior probability distributions with multiple imputations allowed to assess treatment efficacy within and between cohorts. The need for additional endpoints to achieve primary and secondary significance will be determined utilizing longitudinal modeling. Finally, dose response will be modeled and analyzed within and between cohorts to determine optimal therapy dose for stimulation in open label period within and between cohorts using Normal dynamic linear modeling (NDLM) since monotonicity of the response cannot be assumed.

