#### 6.1.2 Primary Effectiveness Endpoint:

The primary effectiveness endpoint is the percent reduction in total body weight loss (%TBWL), measured as End Weight – Initial Weight divided by Initial Weight, multiplied by 100, at the end of Therapy period compared to Baseline between Treatment and Control.

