#### 6.1.3 Secondary Effectiveness Endpoints:

- Number of subjects reporting >5% total body weight loss at the end of Therapy as compared to Baseline between Treatment and Control
- Percent change in appetite scores at the end of Therapy Period compared to Baseline between Treatment and Control.
- Blood pressure, blood lipids, ALT and HbA1c at the end of Therapy Period as compared to Baseline between Treatment and Control groups.
- % changes in BMI at the end of Therapy Period compared to Baseline between Treatment and Control groups

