### 8. STATISTICAL CONSIDERATIONS AND ANALYSIS PLAN

Categorical variables will be summarized by number and percent. Continuous variables will be summarized by total number (N), mean, standard deviation (SD), median, minimum and maximum. Ninety-five percent, 2-sided confidence intervals on estimated means and differences in means between treatment and control groups will be calculated. Confidence intervals will be similarly computed for proportions and differences between proportions. In addition, propensity score and sensitivity analyses will be utilized to compare adverse events and/or adverse device effects incidence versus historical control. Wilcoxon signed rank tests, Fisher exact tests, and Pearson Correlations will be utilized to compare changes in baseline variables between varying

time points of the study (e.g. baseline versus post stimulation treatment) and to correlate stimulation parameters with endpoint values. Markov-chain Monte Carlo Analyses will be utilized to conduct Bayesian posterior probability distributions with multiple imputations allowed to assess treatment efficacy within and between cohorts. The need for additional endpoints to achieve primary and secondary significance will be determined utilizing longitudinal modeling. Finally, dose response will be modeled and analyzed within and between cohorts to determine optimal therapy dose for stimulation in open label period within and between cohorts using Normal dynamic linear modeling (NDLM) since monotonicity of the response cannot be assumed.

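### The plan aims at significance on secondary endpoints, but Section 8 drops the summary's multiplicity correction, no rule is given anywhere, and one secondary (% BMI change) repeats the primary

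*Combined protocol and SAP*

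**What the plan says.** The Protocol Summary (Statistical Analysis) and Section 8 carry almost the same paragraph. Section 8 states: "Ninety-five percent, 2-sided confidence intervals on estimated means and differences in means between treatment and control groups will be calculated", and the sentence ends there. In the summary the sentence continues with a parenthesis, "corrected for multiplicity where needed". Neither text says which comparisons need correcting or how. No other section names a family of endpoints, a testing order, a correction method or a significance level for the secondaries.

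Both paragraphs also say that the need for additional endpoints "to achieve primary and secondary significance will be determined utilizing longitudinal modeling". Section 8.1.2 writes a formal null and alternative hypothesis for appetite, which is a secondary endpoint.

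Section 6.1.3 has four bullets naming seven variables: responders ("Number of subjects reporting >5% total body weight loss at the end of Therapy as compared to Baseline"), appetite scores, blood pressure, blood lipids, ALT, HbA1c, and percent "changes in BMI at the end of Therapy Period compared to Baseline between Treatment and Control groups". The primary endpoint in Section 6.1.2 is percent weight change, "measured as End Weight – Initial Weight divided by Initial Weight, multiplied by 100". Section 9.4 derives BMI from height and weight, and Appendix 6 schedules height at Visit 0 only.

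**The concern.** The summary commits to some correction and the section that an analyst would work from does not repeat it. Restoring the missing parenthesis would not be enough, because it leaves open when a correction is needed and what it would be. Without a stated family and order, the choice of which secondary results count as significant can be made after the data are seen. In a study that its own rationale calls pivotal, that weakens any secondary claim.

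The BMI endpoint adds a second problem. If it tracks the primary exactly, a significant primary brings a significant BMI result with it, and a reader could take the pair as two findings. If a correction is applied across the list, the duplicate uses up part of the error allowance and gives nothing in return.

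**Working it through.** The documents give no family-wise error figure, so there is none to reproduce. The 75 per group in Section 8.2 is sized on the primary endpoint and does not enter here.

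**Inputs.** The per-comparison level is 5% two-sided, read from the 95% intervals in Section 8; no alpha is stated as such. The count is seven variables as named in Section 6.1.3. If blood pressure is taken as two variables and lipids as four (an assumption, since neither is itemised), the count is 1 + 1 + 2 + 4 + 1 + 1 + 1 = 11.

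**Chance of at least one false positive.** With k independent tests and all nulls true, it is 1 − 0.95^k.

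- k = 7: 1 − 0.95^7 = 30.2%
- k = 11: 1 − 0.95^11 = 43.1%

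These variables are unlikely to be independent, since the summary itself describes several as associated with weight loss. The same chance was therefore simulated with equally correlated normal test statistics, 400,000 replicates, each tested two-sided at 1.96:

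| Variables | Independent | Correlation 0.5 | Correlation 0.8 |
|---|---|---|---|
| 7 | 30.2% | 23.0% | 14.8% |
| 10 (11 less BMI) | 40.1% | 28.7% | 17.3% |
| 11 | 43.1% | 30.3% | 18.0% |

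**If the device does change weight.** The BMI and responder nulls would then be false. Five of the seven variables remain, or nine of the eleven: 1 − 0.95^5 = 22.6% and 1 − 0.95^9 = 37.0% under independence.

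**BMI identity.** Let W0 and W1 be initial and end weight and h the single height measurement. Then

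(W1/h² − W0/h²) ÷ (W0/h²) = (W1 − W0) ÷ W0.

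Height cancels, and the right-hand side times 100 is the primary endpoint. A numerical check on 1,000 simulated subjects gave a largest difference of about 2 × 10⁻¹⁴ and a correlation of 1.0.

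**Cost of keeping the duplicate.** A Bonferroni split over seven variables gives 0.05/7 = 0.0071 each, with intervals 1.37 times as wide as uncorrected ones. Without BMI it is 0.05/6 = 0.0083, and 1.35 times as wide.

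**The case against.** The strongest reply is that this is a wording gap and no more. That is partly right, and several stronger readings that a reader might draw are not supported.

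- **That Section 8 contradicts the summary.** It omits the correction; it never says the intervals will be uncorrected. The inconsistency is by omission.
- **That secondary significance drives continued enrolment.** The sentence quoted above concerns a need for additional endpoints, not subjects, and it stands in the summary as well. Section 8.2 ties extra enrolment to projected underpowering of the primary. Section 5 mentions secondary endpoints near cohort sizing, but the link is loose.
- **That the plan declares the secondaries non-confirmatory and then tests them.** No section gives them that label.
- **That the false-positive chance is simply 40%.** That needs ten independent tests. The documents name seven variables, one a duplicate of the primary and another its dichotomised form. Six variables without BMI give 1 − 0.95^6 = 26% even under independence.
- **That the primary result is compromised.** This gap does not touch the primary test's error.

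Other points on the plan's side have some force. Section 8 writes no hypothesis for blood pressure, lipids, ALT or HbA1c, and the summary's rationale calls lipids, ALT and HbA1c both ancillary endpoints and secondary measures, so their status is unclear. Section 8.1.3 groups BMI with the other weight measures under one hypothesis. The BMI identity also needs a common baseline: weight is taken at Visits 0 and 1 without a statement of which is initial, and the Appendix 1 chart rounds BMI to whole numbers. Those details could separate the two variables slightly, but neither would make BMI independent evidence.

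What is left after all this is that significance is sought on secondary endpoints and no rule governs it.

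**Conclusion.** The concern holds as a gap in the control of secondary claims. Following Section 8 as written gives uncorrected secondary inference. If all secondary nulls are true, the chance of at least one false positive is about 30% (seven variables) to 43% (eleven) under independence, and roughly 15% to 30% at correlations of 0.5 to 0.8. Even the lowest of these is about three times 5%.

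The figures rest on a 5% two-sided level per variable, one analysis of each, equal correlations, and an assumed split of blood pressure and lipids for the upper count. They do not count the repeat on completers in Section 8.4 or any interim look. Percent BMI change is the primary endpoint again, provided the same baseline weight is used and BMI is not rounded. This should be repaired before secondary results are analysed, but it is not a threat to the primary conclusion.

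**What to change.** Put one identical rule in the Protocol Summary and Section 8:

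1. Test secondary endpoints only if the primary effectiveness test is significant.
2. Then test, in fixed order and each at two-sided 5%, the responders above 5% weight loss and one named appetite score. Stop at the first that fails.
3. If both succeed, apply Holm at 5% across a listed set of blood pressure, lipid, ALT and HbA1c variables.
4. Report percent BMI change descriptively and outside the tested list.

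For this to be workable the sponsor must say which appetite score is meant (Section 2.1 uses both a weekly VAS and the TFEQ-R18V2), which blood pressure and lipid variables are tested, and which visit supplies the initial weight. The order shown is one reasonable choice; another fixed order set in advance would also serve.

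The acceptable alternative is to label all secondaries exploratory and remove the language of significance for them in both places.

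Either route costs only wording in the protocol and SAP. The price of the first is fewer nominally significant secondary results; the price of the second is that no secondary claim can be made.

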	At the end of the Therapy Period, subjects will complete an end of study visit to be assessed for weight loss, blood pressure, blood lipids, hemoglobin A1c, CMP (Reduction of ALT), patient preference questionnaire and their participation will be considered complete (pending laboratory results, adverse events or serious adverse events).
	The study utilizes an adaptive approach where cohorts of enrolled/randomized subjects (in groups of 25 per arm) are assessed for dose response and progression to achievement of primary and secondary endpoints. Frequent interim endpoint

	assessment utilizing Markov-chain Monte Carlo (MCMC) methods coupled with Longitudinal analyses will be utilized to determine sample sizes for future cohorts (assessed primarily via Normal dynamic linear modeling [NDLM]).
Subject Population / Sample Size	The primary endpoint is powered at a final enrollment of 75 subjects per group, for a total of 150 subjects, but interim analyses based on Bayesian posterior probability distributions with multiple imputation will be utilized to assess interim significance.
	In the event the interim analysis is not significant, up to 300 subjects may need to be enrolled in order to achieve final separation between groups for statistical significance. Thus, Elira may need to screen up to 500 subjects to account for exclusions prior to enrollment.
Study Duration and Sites	Minimum study duration for each patient will be 13 weeks. As it is expected that recruitment of 150 subjects will take up to 12 weeks, the overall study duration is anticipated to be a minimum of 26 weeks, assuming all cohorts are enrolled. The study will be conducted at up to 10 centers.
Inclusion	Subject is between 18 – 65 years of age inclusive.
Criteria	Subject has a BMI of 25-35 kg/ m² inclusive.
	Subject has signed the informed consent form and is able to comply with study protocol and adhere to study visit schedule.
	Subject is able to wear and use a wearable, patch TENS system.
	Subject is able to use a touch screen hand held smart phone.
	Subject is fluent in English and can complete patient questionnaires.
	Subject can comply with a 1200 calorie diet for the duration of the study.
	Subject is male or non-pregnant, non-lactating female, who agrees to use effective contraceptive methods throughout the length of the trial based on PI approval.

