#### 5.1 Dosing Schedule

All Treatment Subjects will be trained in rotation of the patch electrodes every 24h such that it is applied to varying locations on the T6/T7 dermatome. Each active therapy subject will receive up to 30 mA sustained current of stimulation (up to 40mA peak) for 30 minutes after each of three meals per day (delivered within 1-hour post prandially). Based on tolerance of the therapy, a subject may decrease his or her dose by dropping one of the 3 post prandial sessions after receiving approval from a clinical coordinator and/or PI. Subjects who do not experience sufficient appetite suppression may add up to three 15-minute pre-prandial rescue sessions delivered within 2 hours before each meal after receiving approval from a clinical coordinator and/or PI. The nominal stimulation dose per day for any subject will thus be 2400 mA (60 minutes at 40 mA) while the maximum dose for any given subject will be 5400 mA (135 minutes at 40 mA).

During the therapy period, Treatment Subjects will undergo initial assessments to ensure they are familiar with the device, the daily electronic diary, weekly paper diary, and the 1200 calorie diet. All subjects (Treatment and Control) will be required to undergo follow-up assessments at least once per every 4 weeks during the study. Up to two additional unscheduled visits per subject will be permitted during the study. PI will oversee any adjustments to treatment dosing or stimulation parameters.

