#### 5.3 ASSIGNMENT & BLINDING

Subjects meeting the Inclusion and Exclusion criteria will be enrolled and randomized into either Treatment or Control groups. The randomization algorithm will be blocked to account for site bias and to ensure counterbalance across sites. As this is an open label study, there will be no consideration for blinding.

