#### 8.2 JUSTIFICATION OF SAMPLE SIZE

The calculated sample size for the study is based on conservative imputation of results from other studies on weight loss including the use of TENS for weight loss. The degree of coaching/dietary support throughout the present study is moderate intensity lifestyle/weight coaching. The sample size modeling assumes an average of 3.5% TBWL in Control subjects using diet and exercise alone. The estimated weight loss in the Treatment subjects is modeled from preliminary data on T6/T7 dermatomal TENS when used for weight loss: 7.5% TBWL. The variance of the responses in the study (i.e. Standard Deviation) was modeled at + 5% TBWL. This value was taken from previous dermatomal TENS weight loss study results. The model assumes a 30% drop out rate across groups and an 80% powered endpoint using an adaptive p spending model wherein interim posterior probability assessments are allowed after enrolling proscribe cohorts of not less than 25 subjects per group for not less than 7 weeks of stimulation. The alpha penalty will be minimized per interim by assessing the relationship between stimulation (i.e. dose) and weight loss using Normalized Linear Dynamic Modeling (NLDM) to determine overall sample size projected (i.e. futility) rather than assessing the primary endpoint hypothesis per se. Monotonicity will not be assumed in this analysis. This modeling provides an estimate of 75 subjects per group, for a total study size of 150 subjects. However, the protocol allows for enrollment of additional subjects should the interim model project under powering of the primary endpoint.

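### Active dose follows response and tolerance, not randomisation, so the planned dose-response analysis cannot identify an optimal dose and should be labelled exploratory

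*Combined protocol and SAP*

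**What the plan says.** Section 5.3 states that subjects are "enrolled and randomized into either Treatment or Control groups". No cohort or subject is assigned an active dose level.

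Section 5.1 gives every treated subject the same starting schedule, 30 minutes after each of three meals. It then allows two changes, each with coordinator or PI approval:

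- Upward: "Subjects who do not experience sufficient appetite suppression may add up to three 15-minute pre-prandial rescue sessions".
- Downward: "Based on tolerance of the therapy, a subject may decrease his or her dose by dropping one of the 3 post prandial sessions".

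Section 8 models dose response "to determine optimal therapy dose for stimulation in open label period within and between cohorts using Normal dynamic linear modeling (NDLM"), and the Protocol Summary (Statistical Analysis) gives the same purpose. Section 8.1.2 correlates the TFEQ appetite score with stimulation dose, and section 8.1.3 computes confidence intervals for weight loss between stimulation levels. No covariates are named for any of these.

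The only adjustment for confounding named in section 8 concerns safety: "propensity score and sensitivity analyses will be utilized to compare adverse events and/or adverse device effects incidence versus historical control".

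**The concern.** Section 1.3 proposes that stimulation suppresses appetite and that weight loss follows. The trigger for raising the dose is therefore the factor that the protocol itself expects to predict the outcome. Subjects on the longest schedule would tend to be poor early responders, and would tend to lose less weight whatever the extra minutes do. This is confounding by indication, and it arises from the dosing rule. In section 8.1.2 the order is also partly reversed, because a poor appetite response can be the reason for the higher dose.

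Allowing a non-monotone curve does not help. That concerns the shape of the dose-response relation, not who ends up at each dose.

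At stake is a statement about the best dose. Followed as written, the analysis could rank 135 min below 90 min when the extra sessions help, or understate a real gain, and report the result as the optimal dose.

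**Working it through.** The plan states no dose-response figure to reproduce, so the check is how far the section 5.1 rules could distort a comparison of active doses.

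**Dose levels (section 5.1).** Start 3 × 30 = 90 min/day; after a tolerance reduction 90 − 30 = 60; after full escalation 90 + 3 × 15 = 135. Section 5.1 calls 60 min nominal, but three 30-minute sessions make 90, which is used here as the start.

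**From section 8.2.** SD 5 points of %TBWL; 75 per group with 30% dropout, so 75 × 0.7 = 52.5, taken as 52 treated completers.

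**Assumed, not in the documents.** The correlation r between early appetite response and %TBWL; the true gain from 90 to 135 min; and who escalates:

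- Sharp trigger: the lowest third on appetite response escalates.
- Looser trigger: 60% of the lowest third and 10% of the rest escalate (27% overall).

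**Bias formula.** Bias in mean(135) − mean(90) = −r × 5 × F, where F is the mean standardised appetite response of non-escalators minus that of escalators.

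- Sharp: F = φ(z)/(p(1 − p)) with p = 1/3, which is 0.3636/0.2222 = 1.636.
- Looser: non-escalators average +0.248 and escalators −0.682, so F = 0.930.

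**Break-even r = gain/(5F).**

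| True gain | Sharp | Looser |
|---|---|---|
| 1.0 | 0.122 | 0.215 |
| 2.0 | 0.244 | 0.430 |
| 3.0 | 0.367 | 0.645 |

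**Mean contrast, and share of simulated treatment arms (n = 52) ranking 135 below 90, for a true gain of +1.0.**

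| r | Sharp: mean | Sharp: wrong order | Looser: mean | Looser: wrong order |
|---|---|---|---|---|
| 0 | +1.0 | 25% | +1.0 | 26% |
| 0.1 | +0.2 | 45% | +0.5 | 37% |
| 0.2 | −0.6 | 66% | +0.1 | 48% |
| 0.3 | −1.5 | 84% | −0.4 | 60% |
| 0.4 | −2.3 | 94% | −0.9 | 71% |

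The r = 0 row is sampling error alone. For a true gain of +3.0 the wrong-order share over the same range of r runs from 2 to 56% (sharp) or 3 to 24% (looser).

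**Second set of assumptions.** The lowest 25% on appetite response escalate; the lowest 15% on tolerance among the rest reduce; mean 7.5% at 90 min.

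| True effect per 30 min | r, appetite | r, tolerance | Mean at 60 / 90 / 135 min |
|---|---|---|---|
| +0.5 | 0.3 | 0 | 7.6 / 8.1 / 6.4% |
| 0 | 0.3 | 0.3 | 5.8 / 8.5 / 5.6% |
| 0 | 0 | 0.3 | 5.2 / 7.9 / 7.5% |

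In the first row the truly best dose looks worst. In the second a false peak appears at 90 min. In the third the fitted slope is +0.44 per 30 min although the true slope is zero. With both correlations at zero the true slope is recovered, so the distortion comes from the selection rule, and its direction depends on which route dominates.

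**Would adjustment rescue dose selection?** With n = 52, r = 0.2 and true gain +1.0, adjusting for a perfectly measured trigger restores the mean to +1.0. The SE remains 1.75 (looser) to 2.30 (sharp), and the order is still wrong in 28 to 33% of runs. If the measure has reliability 0.7 (assumed), the mean is +0.67 (looser) or +0.18 (sharp).

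**The case against.** **The consequence is limited.** Dose selection is not an objective (section 4) or an endpoint (section 6). Nothing carries an optimal dose into a later cohort, a dosing rule or a success criterion. The phrase also points to an open-label period that the study does not separately have. All of this stands, and it sets the priority low. It does not remove the point, because the Summary and section 8 state a purpose that the data cannot serve.

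**The illustration is not the planned analysis.** It compares final means at two schedules. The protocol also allows intermediate schedules, lets amplitude vary up to a limit, and plans longitudinal modelling. The primary population is modified ITT with last value carried forward, not completers. This stands too, so the figures show what the rules can do and do not forecast a result.

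**A reader might infer that interim decisions are compromised.** Section 8.2 describes "assessing the relationship between stimulation (i.e. dose) and weight loss using Normalized Linear Dynamic Modeling (NLDM) to determine overall sample size projected (i.e. futility"). The documents do not support a claim of wrong sample-size or futility calls. They do not say whether controls enter the model at dose 0. If they do, with means 3.5 (control) and 7.5 (90 min), the slope stays at +1.5 to +1.8 points per 45 min for r from 0 to 0.5, and is negative in at most 0.5% of runs at 25 per arm. If they do not, the effect on a projection has not been worked out. The Summary also says that "interim analyses based on Bayesian posterior probability distributions with multiple imputation will be utilized to assess interim significance". Which method governs is a separate question, and a new interim rule does not follow from this point.

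**Conclusion.** The point holds for the ordering of active doses. Dose received depends on early appetite response and tolerance, no adjustment is planned, and the analysis as written can understate or reverse a real gain from more stimulation.

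How far it does so rests on inputs that the documents do not give: the correlation of early appetite response with %TBWL, the true gain, who escalates, and the amplitude used. Across the assumed cases, reversal on average needs a correlation of anywhere from 0.12 to 0.65. It would therefore go too far to say that the longest schedule must look worst.

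It would also go too far to see a threat to the main result. Treatment versus Control is randomised, and this point does not affect it. What remains is a low-priority correction of wording and interpretation.

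**What to change.** 1. In the Protocol Summary and section 8, replace the optimal-dose purpose and its reference to an open-label period. Suitable wording: *Dose response among treated subjects during the Therapy Period will be described as an exploratory analysis. Because dose follows response and tolerance, no dose will be selected from it.*
2. Label the dose comparisons in sections 8.1.2 and 8.1.3 in the same way.
3. Show each result unadjusted and adjusted for appetite VAS and weight at one early time point defined for every treated subject, for example Visit 2 (week 1), with dose changes before then flagged. State that neither result selects a dose.

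Recording the reason for each dose change is optional, since under section 5.1 the direction of the change largely gives it. Section 8.2 needs no change on this account.

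The cost is wording and a little analysis. Weekly VAS, visit weights and schedule changes are already collected (section 5.2, section 9.8, Appendix 6). The trial gives up its claim to find a dose, which is not one of its objectives or endpoints.
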